Official Title:	Multicenter open-label randomized comparative trial of the efficacy and safety of single bolus injection of Fortelyzin® («SuperGene», LLC) and bolus-infusion of Actilyse® (Boehringer Ingelheim Pharma GmbH) in patients with massive pulmonary embolism (PE)
Short title:	FORPE
Trial phase:	III b
Trial aim:	Assessment of the efficacy and safety of single-bolus intravenous injection of Fortelyzin® in comparison with bolus infusion of Actilyse® in patients with massive PE
Trial objectives:	
• To assess the efficacy of single-bolus intravenous injection of Fortelyzin® in comparison with bolus infusion of Actilyse® in patients with massive PE• To assess the safety and possible adverse events of single-bolus intravenous injection of Fortelyzin® in comparison with bolus-infusion of Actilyse® in patients with massive PE
Trial design:	A multicenter, open-label, randomized, comparative, parallel-group non-inferiority trial of efficacy and safety. In clinical centers, patients will be randomized using the «envelope method» into two equal groups of 155 patients each (a total of 310 people, including 10 % of those who may have dropped out) and assigned to receive either Fortelyzin® or Actilyse®. The drugs will be administered after signing the informed consent. Fortelyzin® in a dose of 15 mg

	
will be given as single i.v. bolus over 10-15 seconds. Actilyse® will be administered in accordance with the instruction for use. Patients will be monitored for 30 days: 1-2 days in the Intensive Care Unit and the Department of cardiology in the remaining days before discharge (on average 14 days), with an outpatient visit on the 30th day.
 
Enrollment of patients into the trial will be conducted on a competitive basis.

Trial duration:	The trial completion date is the 30th day after the final trial patient was included in the trial. All patients will be examined for 30 days
Trial population:	Men and women aged 18 years and older with a diagnosis of massive PE
Sample size:	The total number of patients included in the trial – 310 people, including 10 % of possible dropouts
Study drug:	
Fortelyzin®, registration number – LP001941 as of December 18, 2012.
 
Pharmaceutical form: Lyophilizate for preparation of a solution for intravenous administration, 5 mg (745,000 IU), supplied with a solvent
 
Composition:
 
Active substance: Forteplase® (recombinant protein containing the amino acid sequence of staphylokinase) 5 mg (745,000 IU).
 
Excipients:
 
 L-arginine - 15,0 mg, L-histidine – 2,0 mg, glycine – 30,0 mg, povidone-17: 20,0 mg, polysorbate-20: 0,4 mg.

	Solvent: 5 mL ampule of sodium chloride 0.9%, solution for injection
Inclusion criteria:	
 Men and women aged 18 and older Massive PE (confirmed by CTPA) Signs of RV overload/dysfunction (at least one)¹ associated with persistent hypotension or shock² Patient consent to use reliable contraceptive methods throughout the study and for 3 weeks after: 
 women who have a negative pregnancy test and use the following contraceptives: intrauterine devices, oral contraceptives, contraceptive patch, long-acting injectable contraceptives, double barrier method of contraception. Women who are not capable of bearing children (documented conditions: hysterectomy, tubal ligation, infertility, menopause for more than 1 year) can also take part in the study; men using barrier contraceptives. The study may also include men who are not capable of bearing children (documented conditions: vasectomy, infertility) Signed and dated informed consent from the patient to participate in the trial
Exclusion criteria:	
 Increased risk of bleeding: 
 extensive bleeding at present or within the previous 6 months, hemorrhagic diathesis;

¹

– RV end-diastolic diameter more than 30 mm (parasternal long axis);
– RV/LV end-diastolic diameters ratio more than 0.9;
– hypokinesis of RV-free wall (Mc Connel sign);
– tricuspid regurgitant jet velocity in systole more than 2.6 m/s [1, 2].

²

– cardiac arrest;
– obstructive shock (systolic BP <90 mmHg or vasopressors required to achieve a BP \geq 90 mmHg despite an adequate filling status, in combination with end-organ hypoperfusion);
– persistent hypotension (systolic BP <90 mmHg or a systolic BP drop \geq 40 mmHg for >15 min, not caused by new-onset arrhythmia, hypovolaemia, or sepsis) [1, 2].

	
- intracranial (including subarachnoid) hemorrhage at present or in history, suspicion of a hemorrhagic stroke;- hemorrhagic stroke or unknown etiology stroke in anamnesis;- ischemic stroke or transient ischemic attack within the last 6 months, with the exception of the current acute ischemic stroke within 4.5 hours;- central nervous system diseases in anamnesis (including neoplasms, aneurysm, surgery on the brain or spinal cord);- major surgery or major trauma within the previous 3 months, recent traumatic brain injury;- prolonged or traumatic cardiopulmonary resuscitation (> 2 min), labor within the previous 10 days, recent puncture of an uncompressible blood vessel (eg, subclavian or jugular vein);- severe liver disease, including liver failure, cirrhosis, portal hypertension (including esophageal varices) and active hepatitis;- confirmed peptic ulcer of the stomach or duodenum within the last three months;- a neoplasm with an increased risk of bleeding;- simultaneous treatment with oral anticoagulants, for example, warfarin with INR > 1.3;- arterial aneurysms, defects in the development of arteries / veins;- severe uncontrolled arterial hypertension;- acute pancreatitis;- bacterial endocarditis, pericarditis;- suspicion of a dissecting aortic aneurysm;- any other conditions, in the opinion of the doctor, associated with a high risk of bleeding.
--	---

	
 • Lactation, pregnancy • Known hypersensitivity to Actilyse®, Fortelyzin®.
Trial procedures:	
 • collection of anamnesis, physical examination, measurement of vital signs (blood pressure, respiratory rate, heart rate, SpO₂) • PESI stratification • CTRA for massive PE confirmation • ECG • EchoCG • ultrasound diagnostic system of the inferior vena cava system • venous blood sampling for complete blood count (with platelet count) and biochemical blood analysis (with NT-proBNP level determination), coagulogram (INR, APTT, fibrinogen, D-dimer) • general urine analysis
Efficacy criteria:	
 • Primary efficacy outcome – death from any causes within 7 days • Secondary efficacy outcome – PASP (V₁, V₂, V₄, V₅) • Secondary efficacy outcome – hemodynamic collapse within 7 days • Secondary efficacy outcome – recurrent PE within 7 days • Secondary efficacy outcome – death from PE within 7 days • Secondary efficacy outcome – death from any causes within 30 days • Secondary efficacy outcome – clinical composite of hemodynamic collapse within 7 days + recurrent PE within 7 days + death from any causes within 30 days
Safety criteria:	
 • Safety outcomes – ischemic and hemorrhagic strokes within 7 days • Safety outcomes – bleedings BARC type 3 and 5 • number and severity of SAEs and AEs in organs and systems

Conclusion:	Each research center prepares a report, which is signed by the Principal Investigator and approved by the head of the medical institution, where the center is based. The submission deadline is up to 1 month after the completion of the trial. The statistical processing is carried out by an independent statistical expert according to the case report form.
--------------------	---

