1. BACKGRAUND FOR THE TRIAL

Pulmonary embolism (PE) is a complex clinical problem. The prevalence of PE is high and reaches 30-40 people per 100 000 populations in Russia [1]. PE is one of the leading causes of death, morbidity and hospitalization in Europe [2]. It has been shown that in six EU countries (population about 450 million people), the mortality rate from PE is higher than from AIDS, breast cancer, prostate cancer and road traffic accidents combined, and is 11% of the entire population surveyed [2].

In the Russian Federation, mortality from PE is very high and ranges from 10-30%, depending on modern diagnostics and the use of adequate methods of treatment, primarily thrombolytic therapy.

The indication for thrombolytic therapy is massive PE, defined by size scales and risk stratification. Massive PE is defined in the presence of signs of shock or hypotension, which corresponds to III-V class PESI [1].

In accordance with European [1] and Russian [2] Guidelines for massive PE treatment, the following thrombolytic drugs are used:

- 1) streptokinase according to the standard scheme of administration for 12-24 hours or accelerated scheme for 2 hours;
- 2) urokinase according to the standard (12-24 hours) or accelerated schemes for 2 hours;
- 3) alteplase according to the standard scheme of 100 mg for 2 hours.

The recently completed PEITHO study used the «gold standard» thrombolytic therapy for acute ST-segment elevation myocardial infarction (STEMI) tenecteplase in patients with intermediate-risk PE with signs of right ventricular (RV) disease according to a single bolus administration at a dose of 30-50 mg, depending on body weight. Tenecteplase was shown to be highly effective, combined with a large number (6.3%) of hemorrhagic stroke, which did not allow tenecteplase to be included in the list of recommended thrombolytics for PE [3].

FRIDOM 1 study showed equal efficacy and safety of Fortelyzin®, 15 mg as a single bolus, regardless of body weight, compared with Metalyse® (tenecteplase), administered as a single bolus of 30-50 mg depending on body weight, in patients with STEMI. This study demonstrated the high efficacy of Fortelyzin® and its safety, the absence of major bleeding and hemorrhagic stroke in patients with STEMI complicated by cardiogenic shock [5, 6].

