The results of the FRIDOM1 study showed that the timing of PCI after thrombolysis does not affect the thrombolysis safety.

FRIDOM1 trial confirmed the «non-inferiority» hypothesis. The results of the efficacy and safety endpoints showed that Fortelyzin® administered as a single bolus in a dose of 15 mg regardless of body weight is non-inferiority to Metalyse® administered as a bolus at a dose of 30-50 mg depending on body weight in patients with STEMI no later than 12 hours from the onset of the disease. This trial has demonstrated a similar safety profile.

The Ministry of Health of the Russian Federation conducted an examination of FRIDOM1 trial results and approved updated Fortelyzin® instructions, allowing its

single bolus administration at a dose of 15 mg in patients with STEMI no more than 12 h symptoms onset, including in patients with cardiogenic shock.

Fortelyzin® efficacy and safety monitoring

Continuous monitoring of the Fortelyzin® efficacy and safety is carried out and covers 4123 STEMI patients for the period from June 2013 to March 2015.

The average age of STEMI patients who received Fortelyzin® was 64 years, 610 people were older than 75 years old (72% of the total number of patients were male). According to the localization of myocardial infarction, the patients were distributed almost equally (Table 2).

Table 2. Main characteristics of patients treated with Fortelyzin®

Number of patients	Sex, m/f	Average age, Min-max (years old)	Number of patients > 75 years old	Localization of infarction		Average door-to-needle time Min-max (min)
				anterior	posterior	
4123	2981/1142	64 32–93	610 (15%)	2300	1823	206 40–720

The time from the STEMI symptoms onset to Fortelyzin® administration was 206 minutes. Signs of myocardial reperfusion, according to ECG data, by the 90th minute with a non-invasive strategy were observed in 2542 of 3139 patients (81%), with a pharmacoinvasive strategy – in 826 of 984 patients (83%).

With a pharmacoinvasive strategy, according to coronary angiography, coronary blood flow restoration according to TIMI 3 criteria was observed in 403 of 984 patients (41%), according to TIMI 2 criterion – in 305 patients (31%), in total, according to the sum of TIMI 2-3 – in 708 of 984 patients (72%).

Hemorrhagic stroke occurred in 9 (0,3%) patients with the non-invasive strategy and in 3 patients (0,3%) with the pharmacoinvasive strategy.

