6. TRIAL OBJECTIVES

- To assess the efficacy of single-bolus intravenous injection of Fortelyzin® in comparison with bolus infusion of Actilyse® in patients with massive PE.
- To assess the safety and possible adverse events of single-bolus intravenous injection of Fortelyzin® in comparison with bolus infusion of Actilyse® in patients with massive PE.

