8. DESIGN AND PLAN OF RESEARCH ACTIVITIES

This trial is a multicenter, open-label, randomized, parallel-group, phase III b non-inferiority trial to compare the efficacy and safety of the trial drug.

The trial will include 310 patients with massive PE. The patients will be monitored for 30 days: 1-2 days in the Intensive Care Unit and the Department of cardiology in the remaining days before discharge (on average 14 days), with an outpatient visit on the 30th day.

Start of research, initiation of centers: «_____» 20____

Enrollment of patients: «_____» 20____

Result processing and reporting: «_____» 20____

The enrollment period may be extended to total patient enrollment if a research center fails to enroll the planned number of patients. The end date of the trial is considered to be the end date of the trial in all patients involved.

In each research center, the subject of the trial is assigned a serial number that corresponds to the sequence of patient inclusion in the trial. The serial number is reflected in the CRF. The list of patient's identification is stored in the trial file. Patients are included in the trial only after signing the Informed consent form.

Before the trial, all patients will undergo the following procedures: collection of thorough medical history, signs of hemodynamic collapse, risk stratification to assess the prognosis according to the PESI classification, a physical examination, CTPA, ECG, EchoCG with the definition of PASP, ultrasound diagnostics of the inferior vena cava will be performed; blood and urine samples will be taken for laboratory tests:

- **complete blood count:** hemoglobin, red blood cells, hematocrit, leukocyte formula: neutrophils, eosinophils, basophils, monocytes, lymphocytes, platelets, ESR;
- **biochemical blood parameters:** total protein, creatinine, urea, AST, ALT, CK, NT-proBNP, total bilirubin, glucose, sodium, potassium, total cholesterol, HDL-cholesterol, triglycerides;

- **coagulogram:** fibrinogen, aPTT, INR, prothrombin, D-dimer.
- **general urine analysis:** red blood cells.

After enrollment, patients will be randomized using the «envelope method» into two equal groups of 155 patients each (a total of 310 people, including 10% who may have dropped out) and assigned to receive either Fortelyzin® or Actilyse®. Fortelyzin® will be given as single i.v. bolus over 10-15 seconds. Actilyse® will be administered following the instruction for use.

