11. EFFICACY ENDPOINTS

- Primary efficacy outcome – death from any causes within 7 days;
- Secondary efficacy outcome – PASP (V1, V2, V4, V5);
- Secondary efficacy outcome – hemodynamic collapse within 7 days;
- Secondary efficacy outcome – recurrent PE within 7 days;
- Secondary efficacy outcome – death from PE within 7 days;
- Secondary efficacy outcome – death from any causes within 30 days;
- Secondary efficacy outcome – clinical composite of hemodynamic collapse within 7 days + recurrent PE within 7 days + death from any causes within 30 days.

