18. STATISTICAL ANALYSIS OF TRIAL RESULTS

All indicators entered into the clinical database will be listed for each patient and sorted by group (Fortelyzin® or Actilyse®), patient number and visit.

Statistical analysis was carried out using R Foundation for Statistical Computing и Graph Pad Prism 7, Graph Pad Software Inc (version 4.2). Continuous variables will be presented as mean (SD) or median (IQR). Categorical variables will be presented as n (%) and corresponding 95% Clopper-Pearson confidence intervals (CI).

Mann-Whitney U test will be used to compare continuous variables and the two-sided Fisher's exact test will be used to compare categorical variables.

Odds ratios (ORs) will be estimated and presented with 95% CIs. Outcomes will be considered as statistically significant if the p value will less than 0,05.

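### The synopsis extends the non-inferiority label to safety, but a hypothesis, margin and sample size exist only for death, so a non-significant safety result could be reported as non-inferior safety

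*Combined protocol and SAP*

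**What the plan says.** The Trial design entry of the protocol summary calls FORPE a "parallel-group non-inferiority trial of efficacy and safety". Section 8 is looser: a "non-inferiority trial to compare the efficacy and safety of the trial drug". The safety objective in Section 6 is "To assess the safety and possible adverse events of single-bolus intravenous injection of Fortelyzin", which is a descriptive aim with no hypothesis.

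Section 17 states its null and alternative hypotheses for the primary efficacy criterion. Section 11 defines that criterion: "Primary efficacy outcome – death from any causes within 7 days". The only margin, 10 percentage points, is half the difference between 30% mortality untreated and 10% mortality on alteplase. The sample size of 141 per arm, raised to 155, follows from those mortality figures.

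Section 12 lists the safety outcomes: strokes within 7 days, BARC type 3 and 5 bleeding, and AEs and SAEs. None has a margin, a hypothesis, an expected rate or a power statement. Section 18 compares categorical variables by a two-sided Fisher exact test and adds: "Outcomes will be considered as statistically significant if the p value will less than 0,05". It also plans 95% Clopper-Pearson intervals for proportions and 95% intervals for odds ratios. It plans no risk difference, and it does not say how a non-significant safety comparison is to be read.

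**The concern.** A claim of non-inferiority needs a stated margin and an interval or test set against it. For safety the plan has neither, only a test for a difference. Failing to find a difference in a trial sized for another endpoint does not show that safety is no worse, yet the synopsis label invites that conclusion.

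The protocol's account of the earlier STEMI trial shows that the misreading is realistic. Section 1 says "FRIDOM 1 study showed equal efficacy and safety of Fortelyzin" relative to tenecteplase. Section 2 opens its non-inferiority conclusion with "The results of the efficacy and safety endpoints showed that Fortelyzin", so efficacy and safety endpoints together carry the claim. Table 1 in that section shows 1 v 1 major bleeds among 191 patients per arm and no intracranial haemorrhage in either arm, with p-values for a difference.

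Safety can decide the value of a thrombolytic. Section 1 itself describes an effective one that was kept off the recommended list for PE because of haemorrhagic stroke.

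**Working it through.** **1. What the sample size covers.** Inputs from Section 17: 10% mortality in both arms, margin 10 points, one-sided 2.5%, power 80%. With the plan's formula,

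n = (1.960 + 0.842)² × [0.10×0.90 + 0.10×0.90] / 0.10² = 7.849 × 0.18 / 0.01 = 141.3 per arm.

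The plan states 141, and 141 × 1.10 = 155.1 gives its 155. The figure reproduces, and no safety input enters it.

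**2. What the planned safety test can detect.** The documents give no stroke or serious-bleeding rate for this population, so the rates below are assumptions. Power is that of the two-sided Fisher test at p<0.05, found by summing the binomial probabilities of all significant tables.

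| True rates | 155 per arm | 141 per arm |
|---|---|---|
| 1% v 2% | 2.4% | 1.9% |
| 2% v 4% | 9.2% | 8.0% |
| 3% v 6% | 15.9% | 14.0% |
| 5% v 10% | 31.1% | 27.5% |
| 1% v 3% | 10.5% | 8.5% |
| 2% v 6% | 31.8% | 28.0% |
| 3% v 9% | 52.3% | 47.0% |
| 5% v 15% | 81.3% | 76.5% |

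With 155 per arm, a true doubling from 5% would be non-significant in 100 − 31 = 69% of trials. A tripling from 5% would usually be seen; a tripling from 1% would usually be missed.

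**3. What a non-significant result leaves open.** Newcombe 95% intervals for the risk difference, 155 per arm:

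- 10 v 3 events: p = 0.086, interval −0.1 to +9.7 points.
- 3 v 3 events: ±3.8 points.
- 0 v 0 events: ±2.4 points.
- 8 v 8 events (8/155 = 5.16%): the Wilson limits for each arm are 2.64% and 9.85%, so the half-width is √[(9.85 − 5.16)² + (5.16 − 2.64)²] = 5.3 points. A doubling is an excess of 5.16 points, which lies inside the interval and is not excluded.

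**4. The earlier STEMI trial on the same scale.** For 1/191 v 1/191 the Newcombe interval is about ±2.4 points around a rate of 0.5%. Equal counts there could not exclude an excess several times the observed rate.

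**5. What a real safety margin would need.** Same formula, equal rates of 5%, and an illustrative margin of 3 points: 7.849 × (2 × 0.05 × 0.95) / 0.03² = 829 per arm. With a margin of 5 points: 299 per arm. Both margins are illustrations; the plan names none.

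**The case against.** The strongest reply is that one loose synopsis phrase is resolved by the rest of the plan. The official title says comparative, Section 6 says assess, and Section 17 ties the hypotheses to the primary efficacy criterion. Section 18 nowhere says that p≥0.05 means equal or non-inferior. It also promises 95% intervals for proportions and odds ratios, which would show a reader how imprecise the safety data are. Section 19 has a committee review safety at 25%, 50% and 75% of enrolment. Wording about a past trial is not a rule for this one; Table 1 of that trial also includes a transfusion difference (7 v 20, p = 0.02), and the stroke trial described in Section 1 reports its safety results separately from its non-inferiority claim.

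Much of this stands, and it rules out several stronger readings that a reader might infer:

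- That the plan will treat non-significance as proof of safety. No such rule exists; the documents support only that it could be read so.
- That Section 8 and the safety objective contradict Section 17. Section 8 attaches comparison, not non-inferiority, to safety, and an aim to assess is compatible with Section 17.
- That safety will be reported by p-values alone. Intervals are planned.
- That the trial could not detect a doubling or tripling of serious bleeding in general. At a 5% control rate a tripling would be detected in 81% of trials.
- That equal rates near 5% would just exclude a doubling. The simple Wald half-width, 1.96 × √(2 × 0.05 × 0.95/155) = 4.85 points, suggests this, but the Newcombe interval at 8 v 8 does not bear it out.

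The absence of a powered safety hypothesis is not in itself an error. What survives is that the synopsis claims more than the design provides, and that the planned intervals are compared with no limit and omit the risk difference. Section 18 also gives no rule setting an interval against the margin for death; that is a separate and larger gap, and it does not remove this one.

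**Conclusion.** The point holds for the synopsis label together with the missing interpretive rule in Section 18. As written, a non-significant comparison of strokes or BARC 3/5 bleeding could be reported as non-inferior safety, which the design cannot establish. For the assumed doublings, from control rates of 1% to 5%, a significant result would appear in about 2% to 31% of trials with 155 per arm. These figures rest wholly on assumed rates. The bleeding rates reported in the STEMI background (0.3% to 0.5% for intracranial haemorrhage or major bleeding) are lower and would reduce power further; higher rates would raise it. That no margin exists for safety does not depend on any assumed rate. It should be corrected because the wording limits what the trial may conclude; conduct and sample size are unaffected.

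**What to change.** In the synopsis, limit non-inferiority to the primary outcome, all-cause death within 7 days, and describe safety as a comparative assessment. Section 8 may be aligned for clarity.

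In Section 18, add text to this effect:

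*For strokes and for BARC type 3 or 5 bleeding, the risk difference (Fortelyzin minus Actilyse) will be reported with its 95% confidence interval. A p-value of 0.05 or more will not be taken as evidence of non-inferior, equal or similar safety. The safety conclusion will state the largest excess on Fortelyzin that the interval does not exclude.*

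The cost is wording in two or three places, with no added patients, procedures or data. The downside is a less favourable safety statement in the final report. The alternative, a pre-specified and justified safety margin, would on the illustration above need several hundred patients per arm, so limiting the claim is the practical course.
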